1.12 Table 1: Schedule for evaluation throughout the study

| Description of the procedures according | D0* | D1∞ | D2 | D3 | D4 | D5 | D6 | D7 | D8 | D9 | D10 | D11 | Dx | D14# | D28# |
|--|-----|-----|-----|-----|-----|-----|-----|-----|-----|-----|-----|-----|-----|------|------|
| to the protocol $^{\mu}$ | D0 | Di | D2 | D3 | | | 20 | 2, | | | DIO | | | | D20 |
| Application of ICF ^t | X | | | | | | | | | | | | | | |
| Review of eligibility criteria ^a | X | | | | | | | | | | | | | | |
| Randomization ^b | X | | | | | | | | | | | | | | |
| Demography, medical history, including comorbidities (HAS, DM, dG6PD) and coinfections (HIV, TB, hepatitis) ^c | X | | | | | | | | | | | | | | |
| Physical exam ^d | X | | | | | | | | | | | | | | |
| Clinical evaluation ^e | X | X | X | X | X | X | X | X | X | X | X | Х | X | X | X |
| Evaluation of concomitant medication ^f | X | X | X | X | X | X | X | X | X | X | X | X | X | X | X |
| 12-lead ECG ^g | X | X | X | X | X | X | X | X | Х | X | X | X | X | X | X |
| Blood sample collection for hematology and biochemistry ^h | Х | (x) | (x) |
| Blood sample collection for virology and storage ⁱ | Х | Х | | X | | Х | | X | | | | Х | X | Х | Х |
| Oropharyngeal Swab and Nasal Swab | Х | X | | X | | X | | X | | X | | Х | X | X | X |
| Record of adverse events (serious and non-serious) ^j | X | X | X | X | Х | Х | Х | X | X | X | X | X | X | X | Х |
| Assessment of the primary outcome ^k | | | | | | | | X | | | | | | X | X |
| Record of secondary outcomes ¹ | | X | X | X | X | X | X | X | X | X | X | X | X | X | Х |

Version_2.0_23march2020

| Respiratory evaluation ^m | (x) |
|--------------------------------------|-----|-----|-----|-----|-----|-----|-----|-----|-----|-----|-----|-----|-----|-----|-----|
| Radiological evaluation ⁿ | (x) |

- μ All data from the study procedures will be collected and entered into the RedCap system;
- * Screening and Randomization may occur on the same day. All procedures must be performed before the study intervention;
- ∞ Evaluations and collections should take place after 24 hours of administration of the investigational product;
- τ The Informed Consent Form will be obtained by the study nurse directly from the participant, or in case of no possibility of this occurring (example: loss of level of consciousness), from a family member or legal guardian.
- Dx Days of hospitalization after completion of treatment;

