- # Participant may be hospitalized or discharged. In the latter case, there will be no outpatient return visit and the main outcome will be assessed by telephone. Note: all procedures will be performed during the hospitalization period and will be interrupted if the participant is discharged;
- a Inclusion/exclusion criteria will be fully assessed at visit D1, prior to inclusion. The diagnosis of SARS-CoV2 will occur a posteriori.
- b Randomization will take place in blocks of 4 with 110 participants each. There will be interim reviews when 25%, 50% and 75% of participants are included;
- c A complete medical history will be obtained prior to randomization to include assessments of cardiovascular, metabolic (for example, Type I or II diabetes mellitus), psychiatric (such as depression), renal (such as nephrolithiasis, nephropathy, renal failure) and bone disorders;
- d Physical examination will consist of evaluation of vital signs (heart rate, respiratory rate, systolic, diastolic and mean blood pressure, peripheral oxygen saturation) and signs and symptoms present;
- e Assessments to highlight any visual and/or mental alterations resulting from chloroquine;
- f Avoid administration of other drugs known to prolong the QT interval (ie quinolones, macrolides, ondansetron), as well as various antiarrhythmic, antidepressant and antipsychotic drugs; Avoid administration of other drugs known to prolong the QT interval (ie quinolones, macrolides, ondansetron), as well as various antiarrhythmic, antidepressant and antipsychotic drugs;
- g A 12-lead ECG will be performed in a semi-supine position after resting for at least 5 minutes. The intention is to exclude the development of prolongation in the QT interval or bradycardia;
- h Blood samples will be collected to assess the COVID-19 infection and perform laboratory tests requested by the doctor. In the case of Manaus, the evaluation of the infection by COVID-19 will take place at LACEN-FVS and the others will take place at the Delphina Rinaldi Abdel Aziz Hospital and A & E. In Niterói-RJ all tests will be performed at the hospital. In Mato Grosso do Sul, the evaluation of infection by COVID-19 will take place at LACEN-MS and any others will take place at participating hospitals;

Version 2.0 23march2020

- i Blood samples will be collected for storage in a biorepository for further evaluation of the immune response profile;
- j Evaluated according to the DAIDS table for clinical and laboratory events;

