- k Evaluated and recorded in the hospital's electronic medical record and inserted in the RedCAP system;
- 1 Evaluated and recorded in the hospital's electronic medical record and inserted in the RedCAP system;
- m If a patient needs it, orotracheal intubation will be performed and the parameters of the mechanical ventilator will be recorded daily;
- n Radiology, tomography or nuclear magnetic resonance exams will be performed according to medical request and New Coronavirus Treatment Protocol (2019-nCOV)
- () denotes optional procedure, to be evaluated by the health professional according to clinical needs

[figure not shown]
Version 2.0 23march2020

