The Multicenter Collaboration Group of Department of Science and Technology of Guangdong Province and the Health Commission of Guangdong Province²⁸ based on in vitro evidence and data from unpublished clinical experiments recommended CQ diphosphate tablets, at a dose of 500 mg twice daily for 10 days, for patients with mild, moderate and severe cases of SARS-CoV2 pneumonia, as long as there were no contraindications for the medication. However, to ensure the safe use of the drug, due to its toxic effects, the use of

several precautions was recommended, including blood tests to exclude the development of anemia, thrombocytopenia or leukopenia, as well as serum electrolyte disturbances and/or liver and kidney dysfunction. They recommended (i) a routine electrocardiogram, in order to exclude the development of prolongation in the QTc interval or bradycardia, (ii) conducting interviews to highlight potential visual and/or mental problems and (iii) avoiding administration of other drugs known to prolong the QTc interval (i.e. quinolones, macrolides, ondansetron), as well as various antiarrhythmic, antidepressant and antipsychotic medications.

The CDC²⁹ has a public document on its website suggesting to treat serious infections through hospital admission with oxygen therapy and CQ. The suggested CQ regimen for adults consists of 600 mg of CQ base (6 tablets A-CQ 100 mg), followed by 300 mg after 12 h on day 1, then 300 mg × 2 / given orally on days 2 to 5 days. This document states the need to stop treatment on day 5 to reduce the risk of side effects, considering the drug's long half-life (30 h). Another guidance document from the Italian Society of Infectious Diseases and Tropical Disease (Lombardy section) recommends using CQ 500 mg × 2 a day or HCQ 200 mg for 10 days, although treatment can vary from 5 to 20 days, according to clinical severity.

The fact that so many studies are conducted in parallel using CQ and HCQ suggests that the scientific community is making a great effort to clarify the role of these drugs in reducing the mortality associated with COVID-19, but this effort is probably not yet sufficiently well-coordinated. Thus, clinical trials that study potential pharmacological treatments for COVID-19 must be performed, so that the safety and efficacy of CQ is demonstrated. Related scientific publications are important and timely in view of the growing number of infections and the absence of specific, licensed drugs.

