3. OBJECTIVES AND OUTCOMES

The general objective of the study is to evaluate the clinical efficacy, safety of therapy and reduction of mortality in hospitalized adult patients with severe respiratory syndrome using two different dosages of chloroquine. Objectives and outcomes are shown in table 2.

 Table 2: Objectives and outcomes.

| Objectives | Outcomes | | | | | | |
|--|---|--|--|--|--|--|--|
| Primary | | | | | | | |
| To assess whether the therapeutic regimen of | Reduction of mortality by 50% | | | | | | |
| Group 1 reduces mortality by 50% in the study | | | | | | | |
| population compared to Group 2. | | | | | | | |
| Secondary | | | | | | | |
| - Assess mortality on days 7, 14 and 28 after | - Mortality on days 7 and 14 | | | | | | |
| hospitalization; | - Clinical status of the subject on days 14 | | | | | | |
| - Assess clinical improvement (use of | and 28 | | | | | | |
| supplemental oxygen, ICU stay, length of stay | -Daily clinical status during | | | | | | |
| in the ICU, length of hospital stay, need for OTI | hospitalization | | | | | | |
| and time on mechanical ventilation, radiological | - Need for and duration of supplementary | | | | | | |
| alterations and time taken to improve the | oxygen | | | | | | |
| radiological and resonance pattern); | - Need for and duration of mechanical | | | | | | |
| - Assess the percentage of SARS-CoV2 | ventilation | | | | | | |
| detection in OPS and blood samples on days 1, | - Length of hospitalization | | | | | | |
| 3, 5, 7, 14 and 28 in the study population; | - Data and cause of death (if applicable) | | | | | | |
| Quantify the SARS-CoV2 virus in | - Prevalence of grade 3 and 4 adverse | | | | | | |
| oropharyngeal swab, nasal swab, OPS and blood | events; | | | | | | |
| samples on days 1, 3, 5, 7, 14 and 28 in the study | - Prevalence of serious adverse events; | | | | | | |
| population; | - Leukogram, hemoglobin, platelets, | | | | | | |
| - Alterations in white cell count, hemoglobin, | creatinine, CK, glucose, total bilirubin, | | | | | | |
| platelets, creatinine, glucose, total bilirubin, | ALT and AST on days 1, 3, 5, 7 (while | | | | | | |
| ALT and AST over time. | hospitalized); and on days 14 and 28 (if | | | | | | |
| - Cumulative incidence of serious adverse | patient is able to return to the clinic or is | | | | | | |
| events (SAEs); | still hospitalized); | | | | | | |
| - Cumulative incidence of grade 3 and 4 adverse | - Negative presence of the virus in | | | | | | |

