5.5.4 Costs

There is no additional cost for the research subjects, nor for the institution, and the procedures to be evaluated will be performed according to the routine and individual medical indication.

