9.2 Security instructions

The safety and tolerability of treatments will be assessed based on the registration of Adverse Events (AEs) and the classification of laboratory assessments and vital signs. A severity rating scale, based on the toxicity rating scales developed by the WHO and the National Institutes of Health, Division of Microbiology and Infectious Diseases, will be used to rate the severity of all symptoms, physical examination findings and results of hemoglobin. All laboratory abnormalities - with Grade 2 or greater for biological data - with clinically significant abnormalities (regardless of degree) must be monitored until resolution or until their progression stabilizes.

Virology exams will be carried out at LACEN - AM, linked to the Health Surveillance Foundation, in partnership with the Leônidas & Maria Deane Institute. The coronavirus diagnostic protocols will follow the routine recommended by the Ministry of Health, with RT-PCR.

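### Tables 1 and 2 conflict on follow-up safety bloods (optional by clinical need versus fixed-day outcomes, and no return visit versus return on days 14 and 28), and the protocol does not say which governs

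*Protocol*

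**What the plan says.** Table 1 (section 1.12) has a row headed "Blood sample collection for hematology and biochemistry". It shows a plain X at D0. In the text available the later cells of this row are partly merged, but every mark that can be read after D0 is a bracketed (x). The key below the table states that the bracket "denotes optional procedure, to be evaluated by the health professional according to clinical needs". Footnote h to the row ties the laboratory tests to what the treating doctor requests.

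Table 2 (section 3) treats the same tests as scheduled outcomes. White cells, hemoglobin, platelets, creatinine, CK, glucose and bilirubin are listed together with "ALT and AST on days 1, 3, 5, 7 (while" the patient is in hospital. They are listed again on days 14 and 28 if the "patient is able to return to the clinic or is" still an inpatient.

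For discharged patients, footnote # of Table 1 says: "In the latter case, there will be no outpatient return visit and the main outcome will be assessed by telephone". It adds that study procedures stop at discharge. Section 5.5.2 likewise confines follow-up to the hospital stay. Section 9.2 requires laboratory abnormalities of Grade 2 or above to be followed; they "must be monitored until resolution or until their progression stabilizes".

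Laboratory change over time is a secondary objective (section 1.4.2). Laboratory events are graded as adverse events (Table 1, footnote j) and feed the safety assessment (section 9.2).

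**The concern.** A site could follow Table 1 and take no blood for hematology or biochemistry after D0 unless a doctor asked for it. Another could follow Table 2 and sample every inpatient on days 1, 3, 5 and 7. Both would be complying with the protocol.

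If sampling follows indication, patients who look worse or stay longer are tested more, and silent changes in creatinine, liver enzymes or blood counts are missed in the others. Blinding prevents testing that is driven by knowledge of the arm. It does not prevent testing driven by symptoms, ECG findings, severity or length of stay, and dose may affect all of these. The comparison of laboratory toxicity between doses would then partly be a comparison of how often each arm was tested. A statistical analysis plan cannot recover samples that were never drawn, so the matter has to be settled in the protocol.

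At days 14 and 28 the question is whether discharged patients contribute laboratory values at all.

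**Working it through.** The plan gives no figure on this point, so the main check sets the texts side by side.

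| Question | One place | Another place |
|---|---|---|
| Bloods on days 1, 3, 5, 7 in hospital | Table 1 and footnote h: optional, on clinical need or request | Table 2: outcome on each of these days |
| Bloods on days 14 and 28 after discharge | Footnote # and section 5.5.2: no return visit, procedures stop | Table 2: taken if the patient can return |
| Open Grade 2+ abnormality at discharge | Footnote #: procedures stop | Section 9.2: follow to resolution or stabilisation |

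The first two rows are contradictions and the third is a tension. Section 1.10 (the research team collects care data) and section 9.1 (laboratory results come from the hospital record) fit the Table 1 reading, but neither states an order of precedence.

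The virology blood row of Table 1 has a plain X at D1, D3, D5 and D7. A draw is therefore already scheduled on every inpatient day that Table 2 names for the first week.

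**What indication-driven sampling could do.** The documents give no testing or toxicity rates, so these inputs are assumptions. Let t be the true proportion with laboratory toxicity, the same in both arms, and d1 and d2 the probabilities of detecting it. Undetected cases count as no event. The observed proportions are a = t × d1 and b = t × d2, so the spurious risk ratio is d1/d2 whatever t is:

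- 0.90/0.80 = 1.125 (given as 1.12)
- 0.90/0.70 = 1.29
- 0.90/0.50 = 1.80

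The chance of p<0.05 in that direction, with n = 197 per arm (sections 5.1 and 10.2) and p̄ = (a+b)/2, is

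Φ{ [ |a−b|√n − 1.96√(2p̄(1−p̄)) ] / √[a(1−a)+b(1−b)] }.

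The group size reproduces: (1.96+0.8416)² × (0.2×0.8+0.1×0.9)/0.1² = 196.2, rounded up to 197.

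Example with t = 20%, 90% versus 50% detection: a = 0.18, b = 0.10, p̄ = 0.14. The numerator is 0.08×14.04 − 1.96×0.4907 = 0.161, the denominator is 0.487, and Φ(0.33) = 63%.

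| True toxicity, both arms | 90% vs 80% | 90% vs 70% | 90% vs 50% |
|---|---|---|---|
| 10% | 5.4% | 11.0% | 34.3% |
| 20% | 7.6% | 19.0% | 62.9% |
| 30% | 10.1% | 28.5% | 83.5% |

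With equal detection, a two-sided 5% test would give 2.5% in either direction.

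If detection is incomplete but equal in both arms, the harm is lost sensitivity. For a true 20% versus 10%, power is 80% at full detection and 69%, 55% and 39% at 80%, 60% and 40% detection.

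**The case against.** The strongest reply is that Table 2 may govern. In that case the inpatient days are already fixed and Table 1 merely carries a wrong mark. That is possible, and it limits the claim. A reader might infer that laboratory toxicity will be counted only where a clinician chose to look, but this follows only if Table 1 is followed, and the protocol does not say so. The partly merged row calls for the same caution, although footnote h supports the optional reading.

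It is also fair to say that the trial is double-blind, that all patients are severely ill inpatients likely to be tested often, and that clinical evaluation, ECG and adverse event recording carry a plain X throughout. A large gap in testing between arms is not demonstrated. The larger ratios above mark the end of an assumed range and are not forecasts.

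Three further inferences are tempting but not supported:

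- Section 5.5.4 says that "the procedures to be evaluated will be performed according to the routine and individual medical indication". A reader might take this to override the daily ECG. It is a statement about costs, and Table 1 schedules the ECG plainly.
- Section 2.2 mentions precautions against anemia and other effects, "as well as serum electrolyte disturbances and/or liver and kidney dysfunction", and no laboratory list names an electrolyte. A reader might infer that electrolytes go unmeasured. The section reports an outside group's recommendation, and Table 1 does not itemise biochemistry.
- Section 9.2 might be read as impossible to meet after discharge. It accepts stabilisation as well as resolution, and section 8.1.1 has patients discharged before day 10 contacted on evaluation days. Tension remains, because a contact alone yields no laboratory value.

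**Conclusion.** The point holds as an inconsistency that the sponsor should resolve. Two contradictions stand in the current text: optional versus fixed-day bloods in hospital, and no return visit versus return on days 14 and 28. The second is also in tension with the follow-up rule in section 9.2.

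The consequence is conditional. If sites work from Table 1, the between-dose comparison of laboratory change and laboratory adverse events is open to distortion by severity, symptoms or length of stay. Size and direction cannot be derived from the documents. Under equal true toxicity and assumed detection of 90% against 80% to 50%, the spurious risk ratio is 1.12 to 1.80. Equal but incomplete detection would cost power instead.

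Only secondary safety outcomes are touched. Day-28 mortality is obtained by telephone after discharge and is not affected.

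**What to change.** 1. In Table 1, mark hematology and biochemistry with a plain X on days 1, 3, 5 and 7 while the patient is in hospital, matching Table 2. Keep other days optional, and adjust footnote h so that it no longer limits those four days to tests on request.
2. State that the comparison of laboratory values over time uses the scheduled-day samples. Continue to count every grade 3-4 laboratory event whenever it is found, because restricting events to scheduled days would discard real ones.
3. Reconcile Table 2, footnote #, section 5.5.2 and section 9.2 on days 14 and 28. One option is to limit the laboratory outcomes on those days to patients still in hospital. How the Grade 2+ follow-up rule applies after discharge is for the sponsor to settle, but these passages must agree.

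The cost is an amendment to the two tables and the related text, plus a few extra inpatient panels from draws that Table 1 already schedules. Two limits remain. Patients discharged or dead before a scheduled day still lack a value, and events found on optional days still depend partly on who was tested.

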1.13 Study flowchart

The therapeutic schematic and mortality assessments are shown in figure 1.

Figure 1. Therapeutic scheme for monitoring patients using chloroquine in lower and higher doses.

Dosage:

| Group 1 (higher dosage – 10 days) | | | | | | | | |
|-----------------------------------|-------------------------------------|------------------------------|--|--|--|--|--|--|
| | 1 st daily dose | 2 ^a daily dose | | | | | | |
| D1 – D10 | 4 tablets of 150mg (600mg) | 4 tablets of 150mg (600mg) | | | | | | |
| | | | | | | | | |
| Group 2 (lowe | r dosage – 5 days CQ + 5 days place | ebo) | | | | | | |
| D1 (Loading | 3 tablets of 150mg (450mg) + | 3 tablets of 150mg (450mg) + | | | | | | |
| dose) | 1 tablets of placebo | 1 tablets of placebo | | | | | | |
| D2 – D5 | 3 tablets of 150mg + | 4 tablets of placebo | | | | | | |
| D2 - D3 | 1 tablets of placebo | 4 tablets of placebo | | | | | | |
| D6 – D10 | 4 tablets of placebo | 4 tablets of placebo | | | | | | |

Administration: Oral (or via nasogastric tube in case of orotracheal intubation - OTI)

Placebo: pills without active ingredient but with the same appearance (there will be no exclusive placebo arm) will be used to standardize treatment.

2. INTRODUCTION

2.1 Rationale of the study

COVID-19 is a respiratory disease caused by a new coronavirus (SARS-CoV2) and causes substantial morbidity and mortality. There is currently no vaccine to prevent COVID-19 or infection by SARS-CoV-2 or a therapeutic agent to treat COVID-19. This clinical trial was designed to evaluate the therapeutic effect of chloroquine for the treatment of hospitalized adult patients with severe respiratory syndrome.

2.2 Background

Coronavirus is one of the main pathogens that targets the human respiratory system. Previous outbreaks of coronavirus (CoVs) include severe acute respiratory syndrome (SARS) -CoV and Middle East respiratory syndrome (MERS)-CoV, and are characterized as agents that pose a threat to public health¹. The first cases of the new coronavirus 2019 (COVID-19) were reported in December, 2019, when a group of patients was admitted to hospitals with an initial diagnosis of pneumonia of unknown etiology². From December 18th to 29th, 2019, five patients were hospitalized with acute respiratory distress syndrome and one of them died³. On January 2nd, 2020, 41 hospitalized patients were identified as having confirmed COVID-19 infection, less than half of these patients had underlying diseases, including diabetes, hypertension and cardiovascular disease³. As of January 22nd, 2020, a total of 571 cases were reported in 25 provinces in China⁴. On January 25th, 2020, a total of 1975 cases were confirmed in mainland China, with a total of 56 deaths⁵. On January 30, 773 cases were confirmed in China and 90 other cases were reported in several countries including Taiwan, Thailand, Vietnam, Malaysia, Nepal, Sri Lanka, Cambodia, Japan, Singapore, the Republic of Korea, United Arab Emirates, the United States, the Philippines, India, Australia, Canada, Finland, France and Germany. The case mortality rate was estimated at 2.2% (170/7824)⁶.

The first confirmed case of COVID-19 infection in the United States, on January 19th, led to the description, identification, diagnosis, clinical course and treatment of this case, which includes the patient's initial mild symptoms on presentation and progression to pneumonia on the day 9 of the disease⁷. Italy had 12,462 confirmed cases according to the Istituto Superiore

di Sanità on March 11th and 827 deaths. The average age of those who died in Italy was 81 and more than two-thirds of those patients had diabetes, cardiovascular disease or cancer, or were ex-smokers⁸.

As of March 15th, the World Health Organization (WHO) registered 51,174 confirmed cases, including 15,384 serious cases and 1,666 cases of death in China. Globally, the number of confirmed cases at the time of writing was 51,857 in 25 countries (https://www.who.int/docs/default-source/coronaviruse/situation-reports). In Brazil, there are 428 confirmed cases in 20 states and the DF. The most affected states are São Paulo, with 240 confirmed cases (56.1%), followed by RJ with 45 (10.5%) and the Federal District with 26 cases (6.1%). There are already seven dead in Brazil, five in SP and two in RJ (March 19th, 2020) (http://platform.saude.gov.br/novocoronavirus/). The cases have increased and there is currently no specific antiviral therapy for coronavirus infections. Few treatment studies have been carried out because most strains of human coronavirus cause self-limiting diseases and care is in the form of support. After the severe acute respiratory syndrome (SARS), the coronavirus was identified in 2002 and caused a major global outbreak, there was a growing interest in the development of specific therapeutic agents. Thus, since the SARS outbreak, new therapeutic agents targeting viral entry, proteins, proteases, polymerases methyltransferases have been tested. However, none of them have been shown to be effective in clinical trials. Recent publications have drawn attention to the possible benefit of chloroquine, a widely used antimalarial drug, in the treatment of patients infected with SARS-CoV29-15

Chloroquine sulfate and phosphate salts (chloroquine diphosphate-CQ) are used as antimalarial drugs. Hydroxychloroquine (HCQ), a derivative of CQ, was first synthesized in 1946 by the introduction of a hydroxyl group in CQ and proved to be less toxic (~40%) in its prolonged use, and is therefore recommended to treat chronic diseases, such as systemic lupus erythematosus and rheumatoid arthritis¹⁶. Both chloroquine diphosphate (CQ) and hydroxychloroquine (HCQ) have a bitter taste, but are generally very well tolerated. **CQ can accumulate in tissues, especially the eye, causing retinal toxicity, associated with the use of high doses and prolonged use**^{17,18}. Myopathy has also been associated with the use of CQ¹⁹. For the treatment of malaria, CQ is recommended, in particular, due to its low cost; moreover, for the treatment of the disease few doses are used, and in safe concentrations¹⁹. In In Brazil,

the Ministry of Health guidelines indicate chloroquine diphosphate and other antimalarial drugs as the treatment for malaria and makes them available throughout the country in the health care centers of the Unified Health System (SUS). CQ diphosphate is produced in Brazil and is part of strategic pharmaceutical assistance programs. It is distributed in all states through a well-established distribution network for the treatment of vivax malaria (cause of 90% of malaria in Brazil).

The *in vitro* antiviral activity of CQ was identified in the late 1960s²⁰, ²¹ and the growth of many different viruses can be inhibited in cell culture by both chloroquine and hydroxychloroquine, including SARS-CoV2¹⁵. Some evidence of activity in mice has been found for a variety of viruses, including the human coronavirus OC43, the enterovirus EV-A71 and the Zika virus and influenza A H5N1²²⁻²⁵. Wang et al. showed the effect of chloroquine in vitro, using SARS-CoV2 infected Vero E6 cells at a multiplicity of infection (MOI) of 0.05. The study demonstrated that CQ was highly effective in reducing viral replication, with an effective concentration (EC) 90 of 6.90 µM that can be easily achieved with standard dosing, due to its favorable penetration into tissues, including that of the lung²⁶. The authors described that CQ is known to block infection by the virus, increasing the endosomial pH and interfering with the glycosylation of the SARS-CoV cell receptor. The authors also speculated on the possibility that the known immunomodulating effect of the drug may increase the antiviral effect in vivo²⁶. Thus, according to these authors, CQ is highly effective in controlling infection by 2019-nCoV in vitro and the safety history of CQ suggests that it should be evaluated in human patients suffering from the new coronavirus disease. In a recent publication, Gao et al.²⁷ demonstrated, based on the use of chloroquine by 100 patients, that the effect of CQ diphosphate is superior to the control treatment in inhibiting the exacerbation of pneumonia, improving pulmonary imaging findings and promoting a negative conversion of the virus and reducing the course of the disease.

The Multicenter Collaboration Group of Department of Science and Technology of Guangdong Province and the Health Commission of Guangdong Province²⁸ based on in vitro evidence and data from unpublished clinical experiments recommended CQ diphosphate tablets, at a dose of 500 mg twice daily for 10 days, for patients with mild, moderate and severe cases of SARS-CoV2 pneumonia, as long as there were no contraindications for the medication. However, to ensure the safe use of the drug, due to its toxic effects, the use of

several precautions was recommended, including blood tests to exclude the development of anemia, thrombocytopenia or leukopenia, as well as serum electrolyte disturbances and/or liver and kidney dysfunction. They recommended (i) a routine electrocardiogram, in order to exclude the development of prolongation in the QTc interval or bradycardia, (ii) conducting interviews to highlight potential visual and/or mental problems and (iii) avoiding administration of other drugs known to prolong the QTc interval (i.e. quinolones, macrolides, ondansetron), as well as various antiarrhythmic, antidepressant and antipsychotic medications.

The CDC²⁹ has a public document on its website suggesting to treat serious infections through hospital admission with oxygen therapy and CQ. The suggested CQ regimen for adults consists of 600 mg of CQ base (6 tablets A-CQ 100 mg), followed by 300 mg after 12 h on day 1, then 300 mg × 2 / given orally on days 2 to 5 days. This document states the need to stop treatment on day 5 to reduce the risk of side effects, considering the drug's long half-life (30 h). Another guidance document from the Italian Society of Infectious Diseases and Tropical Disease (Lombardy section) recommends using CQ 500 mg × 2 a day or HCQ 200 mg for 10 days, although treatment can vary from 5 to 20 days, according to clinical severity.

The fact that so many studies are conducted in parallel using CQ and HCQ suggests that the scientific community is making a great effort to clarify the role of these drugs in reducing the mortality associated with COVID-19, but this effort is probably not yet sufficiently well-coordinated. Thus, clinical trials that study potential pharmacological treatments for COVID-19 must be performed, so that the safety and efficacy of CQ is demonstrated. Related scientific publications are important and timely in view of the growing number of infections and the absence of specific, licensed drugs.

